7.12. Final Analysis

All safety and efficacy tables in final analysis will be presented as:-

Description	Placebo Only Pooled	Pegozafermin 15 mg QW	Pegozafermin 30 mg QW Only	Pegozafermin 44 mg Q2W	Placebo (main) and Pegozafermin 30 mg QW (Extension)
-------------	------------------------	--------------------------	----------------------------------	---------------------------	---

Groups “Placebo Only Pooled” and “Pegozafermin 30 mg QW Only” contain subjects who received the same treatment during the Main Study and the Extension Study. Group “Placebo (main) and Pegozafermin 30 mg QW (Extension)” contains subjects who switched to Pegozafermin 30 mg QW treatment in the Extension Study.

Safety summaries for final analysis will be presented by the actual treatment subject received based on the Safety Analysis Set except for subjects who re-randomized to Pegozafermin 30mg treatment group in the Extension Study. Subjects who switched the treatment group at Extension Study will be summarized under “Placebo (main) and Pegozafermin 30 mg QW (Extension)” group.

Final Efficacy analysis (secondary endpoints of Extension Study) will be performed based on the Full Analysis Set with confirmed fibrosis stage F2 or F3 and NAS ≥ 4 at baseline per 3- panel consensus read and by the randomized treatment group in Main Study.

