5.2. Actual Treatment Group

Primary Analysis for Main Study

If a subject receives only placebo doses, then their actual treatment group will be placebo group. If a placebo subject incorrectly received at least one pegozafermin active dose, then they will be counted as the pegozafermin active treatment group in the highest dose group received for safety analysis. If a pegozafermin subject receives at least one dose of pegozafermin active treatment, then the most frequent dose received will be considered as the actual treatment group.

Final Analysis

In the final analysis, the actual treatment arm will be assigned following the same rule as in the primary analysis for Main Study for subjects who were not re-randomized in the Extension study.

The actual treatment group will be assigned as pegozafermin in the highest dose level if subject switched from Placebo to pegozafermin in the Extension Study. However, subjects who switched the treatment in the Extension Study will be summarized under ‘Placebo (main) and

Pegozafermin 30 mg QW (Extension)" group as a separate column in the final safety summaries and efficacy analysis.

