6. ANALYSIS POPULATIONS

For purposes of analysis, the following populations are defined:

Population	Description
Randomized Analysis Set	All enrolled subjects who are assigned a randomization number in the study.
Full Analysis Set (FAS)	All enrolled subjects with confirmed fibrosis stage F2 or F3 and NAS ≥ 4 at baseline per independent review by a 3-pathologist panel who are eligible and assigned a randomization number in the study and received at least 1 dose of IP. For analysis purposes, subjects will be analyzed according to the treatment they were randomized to regardless of actual treatment received.
Safety Analysis Set	All randomized subjects who receive at least 1 dose of IP. In this population, subjects will be summarized based upon the IP actually received, regardless of the IP to which they were randomized.
PK Analysis Set	All subjects in the FAS who have sufficient data to adequately characterize the trough serum pegozafermin concentrations and have no other events or protocol violations that would adversely affect results, such as not completing the full dose. The analysis population for any population PK modeling may be defined separately in a population PK data analysis plan.
MRI-PDFF Analysis Set	All subjects in the Full Analysis Set who have a baseline and at least one follow up MRI-PDFF assessment.

Primary Analysis

- Patient dispositions and screen failure summary will be presented for all subjects screened.
- Baseline characteristics, protocol deviations, medical histories and concomitant medications will be assessed for Randomized Analysis Set.
- All primary, secondary, and exploratory efficacy endpoints of Main Study will be assessed for Full Analysis Set.
- Exposure and safety assessments will be analyzed based on Safety Analysis Set.
- PK endpoints will be displayed and analyzed for all subjects with applicable data in the PK Analysis Set.

Final Analysis

- Protocol deviations and concomitant medications will be summarized based on Randomized Analysis Set including data in Extension Study.
- Exposure and safety assessments will be summarized based on Safety Analysis Set including data in Extension Study.
- PK endpoints will be displayed and analyzed for all subjects with applicable data in the PK Analysis Set.

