7.12.1. Primary endpoint - Adverse Events

All AE summaries in primary analysis for the Main Study (described in Section 7.10.1) will be repeated for in final analysis based on safety analysis set, extend to the pooled data of both Main Study and Extension Study.

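### SAP 7.12 contradicts other parts of the SAP on who belongs in the final placebo and 30 mg QW columns, and on where switchers go for efficacy

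*SAP*

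**What the plan says.** SAP 7.12 gives one five-column layout for every final safety and efficacy table. Two columns, Placebo Only Pooled and Pegozafermin 30 mg QW Only, "contain subjects who received the same treatment during the Main Study and the Extension Study". A third, the switch column, "contains subjects who switched to Pegozafermin 30 mg QW treatment in the Extension Study". The 15 mg QW and 44 mg Q2W columns get no definition beyond their label.

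Other rules on the same tables read differently:

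- **SAP 7.12, next paragraph:** "Safety summaries for final analysis will be presented by the actual treatment subject received based on the Safety Analysis Set". The only exception is for subjects re-randomised to 30 mg.
- **SAP 6:** the Safety Analysis Set is "All randomized subjects who receive at least 1 dose of IP". Entry to the Extension is not required.
- **SAP 5.2:** the final-analysis arm is "assigned following the same rule as in the primary analysis for Main Study for subjects who were not re-randomized in the Extension study". A Main Study discontinuer was never re-randomised, so this rule covers that subject.
- **SAP 7.12.1:** the adverse event summaries are repeated "based on safety analysis set, extend to the pooled data of both Main Study and Extension Study".

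For efficacy, SAP 7.12 uses the FAS "and by the randomized treatment group in Main Study". SAP 5.2 gives switchers a separate column for efficacy as well as safety. SAP 7.12.2 compares the re-randomised 30 mg group with Placebo Only Pooled.

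**The concern.** Only subjects who complete the Main Study go on to the Extension (SAP 3.2). Those who stop treatment before Week 24 are followed at most to Week 24 (Protocol 7.1). They had no Extension treatment, so they cannot have had the same treatment in both parts. On the literal wording, a placebo or 30 mg QW subject who stopped early fits no column, while a 15 mg QW or 44 mg Q2W subject who stopped early still does.

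The frequency and severity of TEAEs and SAEs is the Extension's primary endpoint (SAP 4.2.1), and discontinuation due to TEAEs is one of its safety endpoints (SAP 4.2.3). SAP 7.2 also has the Main Study disposition table redone in the final layout. Programmed from the column definition, these tables would show Main Study discontinuations on 15 mg and 44 mg but none on 30 mg QW or placebo.

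The efficacy sentence raises a separate problem. Grouping by Main Study randomisation puts subjects who have been on 30 mg QW since Week 26 into placebo for the Week 48 comparison of MRI-PDFF, ALT and Pro-C3.

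**Working it through.** **1. Planning inputs (SAP 3.5).** Arms are 42 + 22 + 16 + 64 + 40 = 184, with dropout up to 15%. To check these, I recomputed the stated power (normal approximation, pooled variance, two-sided 0.05, n × 0.85):

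| Comparison | n per arm | Recomputed (NASH resolution / fibrosis) | SAP |
|---|---|---|---|
| 30 mg QW vs placebo | 54.4 vs 54.4 | 93.8% / 91.8% | 94% / 92% |
| 44 mg Q2W vs placebo | 34 vs 54.4 | 87.1% / 84.0% | 87% / 83% |

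All are within about one point, so the arm sizes and dropout rate can be used.

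**2. Subjects with no column on the literal reading.** A common dropout rate d in all arms is my assumption; 15% is the SAP's maximum.

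| d | Placebo, 64d | 30 mg QW, 64d | Total with no column | 15 mg kept, 16d | 44 mg kept, 40d |
|---|---|---|---|---|---|
| 5% | 3.2 | 3.2 | 6.4 | 0.8 | 2.0 |
| 10% | 6.4 | 6.4 | 12.8 | 1.6 | 4.0 |
| 15% | 9.6 | 9.6 | 19.2 | 2.4 | 6.0 |

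**3. Column sizes at d = 15%.** Placebo QW completers number 42 × 0.85 = 35.7. Half of them, 17.85, go to the switch column.

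- Literal reading: Placebo Only = 22 × 0.85 + 17.85 = 36.55; 30 mg QW Only = 54.4.
- Safety Analysis Set reading: Placebo Only = 22 + 42 × 0.15 + 17.85 = 46.15, of whom 64 × 0.15 = 9.6 are discontinuers (20.8%). 30 mg QW = 64, of whom 9.6 are discontinuers (15%).
- The switch column has no Main Study discontinuers on either reading, because re-randomisation follows Main Study completion (SAP 3.3).

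The Placebo Only discontinuer share is 3.2/44.05 = 7.3% at d = 5% and 6.4/45.1 = 14.2% at d = 10%.

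**4. Effect on adverse event rates.** The documents give no rates, so these are assumptions.

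- *AEs leading to discontinuation in the Main Study.* If 40% of discontinuers stop for an AE, the 30 mg rate is 0.15 × 0.40 = 6% on the full set (4% at d = 10%, 2% at d = 5%). On the literal reading it is 0% whatever share is assumed, since nobody in the column stopped in the Main Study.
- *Any TEAE.* Take 70% incidence in completers and d = 15%. Full-set incidence on 30 mg is 0.85 × 70% + 0.15 × p, where p is the incidence in discontinuers. For p = 50%, 70% and 90% this gives 67%, 70% and 73%. The literal reading gives 70% each time, so the error has no fixed sign.

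**5. Efficacy grouping.** Planned switchers in placebo are 21/64 = 32.8%. Common dropout leaves this unchanged (17.85/54.4 = 32.8%). If switchers show a fraction f of the drug effect at Week 48 (assumed), the contrast with placebo is multiplied by 1 − 0.328f: 0.84 at f = 0.5 and 0.67 at f = 1.

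**The case against.** The best defence is that the SAP already answers the question. The paragraph after the column definition, with 5.2, 6 and 7.12.1, places every dosed subject who was not re-randomised by actual treatment. In that context 'Only' most naturally separates non-switchers from switchers. The 15 mg and 44 mg columns need no such label because nobody switches to those doses. Redoing the disposition table in this layout (SAP 7.2) presupposes that discontinuers are in it. On efficacy, grouping by randomisation may simply contrast with the as-treated safety basis, and 7.12.2 names the intended comparison.

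Much of this stands. A reader might infer that the plan removes Main Study discontinuers, understates adverse events in general and tilts the dose comparison towards 30 mg. The documents do not support that:

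- No section says discontinuers are excluded, and several keep them.
- The effect on overall TEAE incidence has no fixed direction (step 4).
- The column rule treats placebo and 30 mg QW alike, so any favourable look for 30 mg is against 15 mg and 44 mg, and is clear only for AEs leading to discontinuation.
- The switch column also holds only completers, so the absence of discontinuers is not confined to two columns.
- The primary-analysis tables use the full Safety Analysis Set and include TEAEs leading to discontinuation (SAP 7.10, 7.10.1). The events are reported there in any case.

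What does not stand is that clear text elsewhere makes the sentence harmless. It is the SAP's only definition of these two columns, it governs all final tables, and nothing says which rule prevails.

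**Conclusion.** The point holds as an internal contradiction that should be corrected before the final tables are programmed. It is not a settled exclusion.

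For safety, the literal definition would leave about 9.6 of 64 subjects in each of the placebo and 30 mg QW arms without a column at 15% dropout, and about 3 of 64 at 5%. Its one certain consequence is that Main Study AEs leading to discontinuation would read zero in those two columns of the final tables. The direction for overall TEAE incidence is unknown.

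For efficacy, the grouping sentence taken literally would put the planned 21 switchers, 33% of 64, on active drug inside the Week 48 placebo group, against 5.2 and 7.12.2.

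The counts rest on planned arm sizes, equal dropout across arms and 1:1 re-randomisation of placebo QW completers. Actual numbers will differ, and the FAS will be smaller if some randomised subjects fail the three-pathologist read.

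**What to change.** Amend SAP 7.12 as follows.

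1. Define Placebo Only Pooled and Pegozafermin 30 mg QW Only as all subjects in the relevant analysis set on that treatment who did not switch to 30 mg QW in the Extension, including those who stopped in the Main Study. The relevant set is the Safety Analysis Set by actual treatment for safety, and the FAS by randomised treatment for efficacy.
2. Replace the efficacy grouping phrase with: by randomised treatment, with subjects re-randomised to 30 mg QW as a separate group.
3. Add a note that only Main Study completers move to the switch column, so Placebo Only is enriched for discontinuers (about 20.8% against 15% in the other arms at 15% dropout).
4. Show the switch group's placebo-period and active-period events separately.

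The cost is SAP wording and table specifications, with no new data. Rates of discontinuation for AEs in the placebo and 30 mg QW columns would be higher than on the literal reading, and would count every dosed subject who did not switch.

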7.12.1. Primary endpoint - Adverse Events

All AE summaries in primary analysis for the Main Study (described in Section 7.10.1) will be repeated for in final analysis based on safety analysis set, extend to the pooled data of both Main Study and Extension Study.

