6. INVESTIGATIONAL PRODUCT

IP is defined as pegozafermin or matching placebo, intended to be administered to a study subject according to the study protocol.

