5.5. Treatment Emergent Adverse Event (TEAE)

TEAE during the Main Study

All AEs started or worsened within the first dose of IP up to the min of (the last dose date before the completion of all Week 24 assessments in the Main Study IP+28 days, the date all Week 24 assessments completed, Main Study cut-off date) will be considered as TEAEs during the Main Study. For subjects who withdraw consent from the Main Study, the end date of the TEAE reporting period should be the earlier of the withdrawal consent date and the date of the last dose of the IP + 28 days.

TEAE during the Study

All AEs that started or worsened on or after the first dose of study IP up to the last dose of the study IP+28 days will be considered as TEAEs.

For subjects who withdraw consent from the study, the end date of the TEAE reporting period should be the earlier of the withdrawal consent date and the date of the last dose of the IP + 28 days.

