6.2. Analysis Visit Windows

In general, scheduled visits from randomization (except for early terminated subjects) will be used as analysis visit for descriptive analysis tables and listings. Unscheduled visits, ET visit, and EOS visit will be mapped according to the actual study day and analysis visit window defined in [Table 4](#).

Scheduled visit will be selected for analysis/summaries if has valid assessment result. If a scheduled visit is missing, the unscheduled visit that is closest to the target study day will be used for analysis purpose.

Table 4: General Analysis Visit Window

Study Period	Target Study Weeks	Target Study Day	Analysis Visit Window (Days)
Screening Period	-12 to 0	--	--
Main Study	--	1	--
	4	29	2 to 43
	8	57	44 to 71
	12	85	72 to 99
	16	113	100 to 141
	24	169	142 to min (the date all Week 24 assessments completed, Main Study cut-off date)
Extension Study	26	183	•
	30	211	(W24 End date+1) to 239
	38	267	240 to 302
	48	337	303 to 351
Follow-up Period	ET	--	--
	51/EOS	358	>= 352

Week 26 is the start visit for the extension study dosing, no need to be included in the visit-based summary tables if no data is collected.

For parameters with scheduled visit(s) at Week 12 and Week 24, or Week 24 only, the analysis window will be adjusted such that:

- The first post-baseline scheduled visit will start at day 2. Other visits start from the end of previous visit + 1 day.
- The end of each analysis visit window will be middle to the next scheduled visit (If an even number of days exists between two consecutive visits then the end date will be taken as the midpoint value minus 1 day).

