7. STATISTICAL METHODS OF ANALYSES

7.1. General Considerations

The primary analysis will include data up to the min of (28 days after the last dose date before the completion of all Week 24 assessments, the date all Week 24 assessments completed, Main Study cut-off date).

At final analysis, safety summaries including extent of exposure will report data from both Main Study and Extension Study, based on safety analysis set.

Continuous variables will be summarized by number of patients, mean, standard deviation (SD)/ standard error (SE), median, minimum, and maximum values. Minimum and maximum will be presented to the same number of decimal places as reported/collected. One additional decimal place will be presented for mean and median. Two additional decimal places will be presented for SD/ SE up to a max of three decimal places.

Categorical variables will be summarized by number and percentage of patients. Percentage will be presented to one decimal place. The number of missing values will be presented as a separate category with no percentage, but only if 1 or more patients are missing data for the summary. Otherwise, all categories will be presented (even if no patients are counted in the category). Counts of zero in any category will be presented without percentage.

For analysis purpose, placebo QW and placebo Q2W will be pooled except for exposure summaries and pre-specified supportive analyses.

All statistical tests will be 2-sided and tested at a statistically significant level of 0.05 without adjustment for multiplicity. Confidence intervals will be 2-sided 95%, unless stated otherwise. Two-sided p-values will be presented with four decimal places and values less than 0.0001 will be presented as <.0001.

Both reported units (CN) and standard units (SI) will be presented in listings. Only CN units will be used for tables and figures, unless otherwise specified. Insulin will be presented with conventional unit of μ IU/mL.

All applicable analyses for the primary analysis of the Main Study will be presented as:

<Description>	Placebo Pooled	Pegozafermin 15 mg QW	Pegozafermin 30 mg QW	Pegozafermin 44 mg Q2W
---------------	-------------------	--------------------------	--------------------------	---------------------------

A total column will be presented for the disposition, demography, protocol deviation, medical history, prior/concomitant medication/procedure, and other subject information summaries.

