7.10.1. Adverse Events

Subject incidence of TEAEs will be tabulated by MedDRA (Version 24.0) system organ class, MedDRA preferred term, and treatment groups. All TEAEs, all treatment-emergent related AEs, all TESAEs, and all treatment-emergent serious related AEs, the most severe Common Terminology Criteria for Adverse Events (CTCAE) grade, TEAEs leading to dose interruption, TEAEs leading to IP discontinuation, and TESAEs leading to IP discontinuation will be summarized. Subjects will be counted only once within a SOC and Preferred Term (PT), even if the subject experienced more than one TEAE within a specific SOC and PT, and PT only.

Selected TEAE analyses will be repeated in subgroups including age, sex, race, and BMI.

All AEs, SAEs, AEs leading to IP interruption or discontinuation, fatal AEs, and COVID-19 related AEs will be listed with TEAE flags included.

Clinical Laboratory Parameters

Clinical laboratory tests listed in ([Clinical Laboratory Tests](#)) will be collected during the study.

For all other assessments that are below the lower limit of quantification will be imputed to half of the lower limit of quantitation (LLOQ) for summarization; assessments that are above the upper limit of quantification will be imputed to the upper limit of quantitation (ULOQ) for summarization. For listings, records that are LLOQ or ULOQ will be listed as such together with the imputed value in separate columns.

For all hematology, biochemistry urinalysis tests, coagulation factors, lipid assessments, and selected other laboratory assessments, descriptive summaries of absolute values and change from baseline at each scheduled assessment will be produced by treatment groups, the number and percentage of subjects with abnormal laboratory values will be summarized.

Shifts (low/normal/high) from the relevant baseline tables based on the normal ranges will be constructed. The shifts will be performed from the baseline to each post-baseline visit, and to minimum and maximum post-baseline visit.

A summary of suspected liver injury cases according to drug induced liver injury (DILI) criteria will also be presented ([Table 6](#)).

Table 6: Suspected liver injury cases according to drug induced liver injury (DILI) criteria

Baseline Value of ALT/AST	Criteria to discontinue investigational product
>ULN and <2× ULN	ALT or AST >5× baseline value
>=2× ULN but <5× ULN	ALT or AST >3× baseline value
>=5× ULN	ALT or AST >2× baseline value

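### The final adverse event tables give no on-pegozafermin incidence for the placebo-to-30 mg QW switchers, and the re-randomized comparison has no AE table

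*SAP*

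**What the plan says.** - **TEAE window.** SAP 5.5 defines study-wide TEAEs as "All AEs that started or worsened on or after the first dose of study IP up to the last dose of the study IP+28 days". Protocol 6 states that "IP is defined as pegozafermin or matching placebo".
- **Tables.** SAP 7.12.1 repeats the 7.10.1 summaries on the Safety Analysis Set, to "extend to the pooled data of both Main Study and Extension Study". Under 7.10.1 a subject counts once per system organ class and preferred term, and the most severe CTCAE grade is shown.
- **Switchers.** SAP 7.12: "Subjects who switched the treatment group at Extension Study will be summarized under" one column that combines placebo in the Main Study with 30 mg QW in the Extension. No split by period is specified. SAP 6.2 places the change of treatment: "Week 26 is the start visit for the extension study dosing".
- **Stayers.** Also in SAP 7.12, the *Placebo Only Pooled* and *30 mg QW Only* groups "contain subjects who received the same treatment during the Main Study and the Extension Study". SAP 7.1 gives the pooling rule: "For analysis purpose, placebo QW and placebo Q2W will be pooled except for exposure summaries and pre-specified supportive analyses".
- **Endpoint.** SAP 4.2.1 makes frequency and severity of TEAEs and SAEs the Extension's primary endpoint.
- **What is split by drug.** For switchers, exposure and compliance (SAP 7.7) are derived separately for placebo and pegozafermin, and a separate disposition table (SAP 7.2) reports pegozafermin discontinuations.

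**The concern.** There are two separate gaps.

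1. **No on-drug incidence for switchers.** A switcher who has a given preferred term while on placebo is already counted before the first active dose, and the worst grade shown may come from either treatment. The column counts subjects with the event in either phase, so it can only equal or exceed the on-drug incidence. The Main Study tables do not allow it to be recovered by subtraction: they pool all 64 planned placebo subjects, and their TEAE window closes no later than completion of the Week 24 assessments, before the switch at Week 26.

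2. **No randomized AE contrast.** The natural comparator for the switchers is the placebo QW group re-randomized to placebo. Those subjects sit in *Placebo Only Pooled* with the placebo Q2W arm, which was never re-randomized, and they too are counted from Week 0. Correcting the window alone would leave this gap open.

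At stake is whether the Extension's primary endpoint can be read directly for the only subjects who first meet the drug in the Extension. As written, a reader has to rebuild that from listings.

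**Working it through.** **Group sizes.** Placebo QW has 42 planned subjects; 42 / 2 = 21 per re-randomized group, as the SAP states. *Placebo Only Pooled* is then about 21 + 22 = 43, of which re-randomized stayers are 21/43 = 49%. With the SAP 3.5 dropout allowance of 15% applied before the switch, 21 × 0.85 = 17.9, about 18 per group.

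**Days in the switch column.** Target days are from SAP Table 4; the last QW dose is at Week 47 (schedule of activities).
- First active dose, Week 26: Day 183
- Last dose, Week 47: 47 × 7 + 1 = Day 330
- End of TEAE window: 330 + 28 = Day 358
- Before the first active dose: Days 1 to 182, so 182 days
- From the first active dose: 358 − 183 + 1 = 176 days
- Share before pegozafermin: 182/358 = 50.8%

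In doses, Weeks 0 to 25 are 26 placebo doses and Weeks 26 to 47 are 22 active doses.

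**Why subtraction fails.** At target dates the Main Study TEAE window closes at Day 169. Placebo Days 170 to 182 (182 − 169 = 13 days) belong neither to that window nor to the on-drug period. The gap falls to 0 if the biopsy is at +14 days, but pooling of all placebo subjects in the Main Study tables remains.

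**Illustration of the effect.** The documents give no AE rates and plan no AE risk ratio, so the per-phase risks below are assumptions: rp on placebo, rd on drug. Under independence between phases, the switch column shows 1 − (1 − rp)(1 − rd) and *Placebo Only* shows 1 − (1 − rp)². Under full within-subject overlap, they show rd and rp.

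| rp, rd | Dependence | Switch column | Placebo Only | Ratio | Difference |
|---|---|---|---|---|---|
| 10%, 20% | Full overlap | 20% | 10% | 2.0 | 10 points |
| 10%, 20% | Independence | 28% | 19% | 1.47 | 9 points |
| 20%, 30% | Full overlap | 30% | 20% | 1.5 | 10 points |
| 20%, 30% | Independence | 44% | 36% | 1.22 | 8 points |

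The full-overlap rows show no distortion. The independence rows show a column 8 to 14 points above the on-drug risk and a ratio pulled towards 1; the difference hardly moves.

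**Denominator for any rate.** SAP 7.7 exposure on drug is 330 − 183 + 7 = 154 days, against a 176-day AE window. Since 176/154 = 1.14, a rate using 7.7 exposure would be overstated by 14%.

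**Precision of a split table.** The exact two-sided 95% upper limit for zero events is 1 − 0.025^(1/21) = 16.1% at n = 21 and 1 − 0.025^(1/18) = 18.5% at n = 18.

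**The case against.** The case for leaving the tables alone has several fair parts.

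- The Extension's objective is long-term safety, which rests mainly on the columns treated throughout with pegozafermin: 16 + 64 + 40 = 120 planned subjects, none affected. Switchers receive only about 22 active doses. Early 30 mg QW safety is already randomized at 64 versus 64 in the Main Study. **This stands** and limits the importance of the point.
- Protocol 4.2 gives the purpose of re-randomization as replication of biomarker effects, and neither document promises a randomized AE contrast. **This stands.** SAP 7.12.2 pools placebo in the same way for the Week 48 MRI-PDFF, ALT and Pro-C3 comparisons, which is closer to that purpose. That does not supply the missing AE table.
- The switch column is labelled as mixed, all AEs are listed with TEAE flags, and about 21 subjects can be reviewed by hand. The label prevents misreading but gives no on-drug incidence. Rebuilding it from listings would be post hoc for a primary endpoint.
- The illustration rests on assumed rates, and on the difference scale it moves by 1 to 2 points, less than one subject in 21 (4.8 points). **This stands.** The finding rests on the counting rules, not on the illustration.
- Table shells are in separate documents that were not available, so a split there cannot be excluded. The SAP text does not call for one.

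**Conclusion.** The point holds for the SAP text. Followed exactly, the rules produce a switch column in which 51% of the planned window precedes pegozafermin and which cannot be read as incidence or worst grade on drug. The re-randomized 21 versus 21 contrast is not tabulated for AEs. The day counts assume target visit dates and completion of dosing, and the group sizes are planned numbers.

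The 15 mg, 30 mg Only and 44 mg columns, the Main Study tables, the AE listings, the switcher disposition table and the by-visit laboratory shifts are unaffected. This is a worthwhile, inexpensive addition to the reporting of the Extension's primary endpoint, not a flaw in the main safety evidence.

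**What to change.** In SAP 5.5 and 7.12.1:

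- Add a treatment-at-onset flag based on the date of the first re-randomized dose (Week 26). A Main/Extension flag at Week 24 would assign the placebo doses of Weeks 24 and 25 to the drug.
- Add one descriptive AE table (incidence and worst CTCAE grade) of events that start or worsen from that dose to the last dose plus 28 days. Show two columns over the same window: switchers, and subjects re-randomized to placebo QW.
- If an exposure-adjusted rate is added, use time at risk in that same window for both groups. SAP 7.7 exposure does not match the window and is not derived after Week 26 for placebo stayers.
- Optionally, apply the same split to the minimum and maximum post-baseline laboratory shifts.

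Keep all existing columns unchanged. The cost is SAP wording, one flag and one or two programmed tables. With about 18 to 21 subjects per group, the table is descriptive only and adds little on long-term safety.
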